Single-center retrospective cohort study: «Evaluation of the Efficacy and Safety of Surgical and Endovascular Interventions on the Pelvic Veins in Pelvic Venous Disorders»

Document Date: March 22, 2021

Study Protocol

Project summary

Surgical and endovascular interventions on the pelvic veins in patients with pelvic venous disorders (PeVD) have been used for a long time. Resection and embolization of gonadal veins (GV) successfully relieve symptoms and signs of pelvic venous congestion in 60-100% of patients. At the same time, to date, there are no convincing data on the obvious advantages of any of the methods, no comparative studies on this problem have been carried out. Iliac vein stenting in patients with a combination of May-Turner syndrome and pelvic congestion syndrome is effective in restoring patency of the left common iliac vein. However, it is not clear whether it is necessary to perform simultaneous iliac vein stenting and gonadal vein embolization in such patients, or whether stenting alone is sufficient.

In addition, highly conflicting data are available regarding the complication rates of various pelvic vein interventions.

Aims of the study: To evaluate the efficacy and safety of surgical and endovascular interventions on the pelvic veins in patients with PeVD, assess complication rates after gonadal vein embolization (GVE) with coils, gonadal vein resection (GVR) and stenting of the common iliac vein using clinical, ultrasound and radiological techniques.

Patients and methods: A total of 300 female patients with PeVD aged who underwent open retroperitoneal resection of the gonadal veins and endoscopic trans- and retroperitoneal resection of the gonadal veins, embolization of the gonadal veins with coils and stenting of the common iliac veins, or stenting of the iliac veins in combination with embolization of the gonadal veins with coils were planned to be enrolled in the period from 2000 to 2021.

Treatment

Gonadal vein embolization with coils

GVE was performed under local anesthesia with 5.0-10.0 mL of 0.5% lidocaine solution with a patient under intravenous sedation. For the left GV embolization, the transfemoral approach was used, while for the right or both GV embolization, the transjugular approach was used. The vein puncture was performed under ultrasound guidance. The 5F multipurpose angiographic catheters (Cordis; USA), standard ‘moving core’ J .035” guidewire, and an angled hydrophilic guidewire

(Radiofocus; Terumo Corp., Japan) were used. For the GV occlusion, the pushable 0.035" standard stainless steel coils (Gianturco; William Cook, Bjæverskov, Denmark) and 0.035" coils made of Inconel with interwoven long collagen fibrils (MReye; Cook Medical Inc., Bloomington, USA) were used. The diameter of coils was 8-12 mm, and the length was 10-20 cm. When selecting the coil size, the principle of 20% coil oversizing relative to the GV diameter was used in order to avoid coil migration in the conductive veins and pulmonary artery. After embolization, the control ovarian venography was performed.

Open retroperitoneal GVR

The procedure was performed under general anesthesia in the reverse Trendelenburg position, on the back with the operating table rotating 30° to the right or left, depending on the side of the GV lesion. The retroperitoneal approach was employed in the left and/or right iliac region (depending on the side of the GV lesion) with an incision of 5 to 7 cm, the GV was mobilized for 10-12 cm and its tributaries were ligated. The vein was ligated at the caudal and cranial segments and resected. Surgical wound was sutured in layers. Drainage of the retroperitoneal space was not used.

Transperitoneal endoscopic GVR

The procedure was performed under general anesthesia in the reverse Trendelenburg position, on the back with the operating table turning 30 ° to the right or left, depending on the intervention side. After carbon dioxide (CO₂) insufflation into the peritoneal cavity (intraabdominal pressure 12 mm Hg), three ports were placed: one 10-mm port in the umbilical region, one 5-mm port in the left or right iliac region, and one 5-mm port 5 cm below the umbilicus. The parietal peritoneum was dissected, the GV was mobilized over a length of 10-12 cm, the GV tributaries were ligated, the caudal and cranial segments of the vein were clipped or ligated, and the vessel was resected. The wounds were sutured, and no drainage was used.

Retroperitoneal endoscopic GVR

The procedure was performed under general anesthesia, and the carbon dioxide insufflation into the retroperitoneum (pressure 12 mm Hg) was applied using a Veress needle in a patient lying on the left or right side in the reverse Trendelenburg position. A 10-mm camera port was installed in the lumbar region between the posterior superior iliac spine and the lower edge of the XII rib. Then one or two 5-mm instrument ports were installed. The GV was mobilized over a length of 10-12 cm, the GV tributaries were ligated, the caudal and cranial segments of the vein were clipped, and the vessel was resected. The wounds were sutured, and no drainage was used.

Stenting of the left common iliac vein

After providing local anesthesia, the left common femoral vein was punctured, a 0.035" guidewire was inserted into the inferior vena cava (IVC), and then a 10F introducer was installed. A balloon catheter was introduced over the guidewire in the left CIV (XXL balloon, Boston Scientific,

diameter 14-18, length 40-60 mm), and double balloon dilation of the vessel was performed with a pressure of 6-8 atm. Then, a delivery system was advanced to the area of stenosis in the left CIV, and stent was deployed at the level of confluence of the left CIV and inferior vena cava (IVC) or with a protrusion in the IVC of no more than 1 cm. For better fixation of stent in the venous lumen and prevention of its displacements and migration, a balloon post-dilatation of the stented vessel was performed. In case of residual stenosis, the balloon angioplasty was performed. A control multiplanar phlebography was repeated thereafter.

All interventions were performed in surgical clinic settings. The routine anticoagulation to prevent thromboembolic complications after the procedure was not prescribed. All patients used antiembolism compression stockings before and after the interventions. Patient mobilization after GVE or GVR started 2 hours after the intervention.

Assessment of the GVE, GVR and stent placement complications

Pelvic venous disease (PeVD), caused by dilation and valvular incompetence of the gonadal, parametrial and uterine veins, often manifests with chronic pelvic pain (CPP), coital and postcoital pain, and dysuria [1,2]. Main treatment goals in such patients are pelvic pain relief and recovery of venous outflow from the pelvic organs [3,4]. Numerous studies have shown that reduction in blood flow in the gonadal veins (GV) using endovascular occlusion or surgical resection is accompanied by a substantial relief or elimination of the PeVD symptoms and signs [5,6].

Gonadal veins embolization (GVE) with nitinol or platinum coils is widely used in the treatment of PeVD [7,8]. Most authors report a high efficacy of this technique in reducing blood flow in the GV and relieving symptoms and signs [9,10]. Clinical practice guidelines of the Society for Vascular Surgery (SVS) and the American Venous Forum (AVF) consider GVE as a standard treatment for PeVD (grade 2B due to moderate-quality evidence) [11]. Another effective treatment for PeVD is gonadal veins resection (GVR) performed using open retroperitoneal or endoscopic approaches [12-14]. Despite the priority given to GVE with coils in clinical guidelines and international consensus documents [2,11], there is no clear evidence, or rather conclusive trials showing that GVE has a higher clinical efficacy compared to GVR. The issue is specifically about clinical efficacy (i.e. relief of the PeVD symptoms and signs) and not the technical success of GVE (occlusion of GVs and elimination of reflux in them), technique of the intervention under local anesthesia, or aesthetic aspects of the procedure (absence of postoperative scars). The main argument of GVE advocates is that GVR is a traumatic intervention requiring general anesthesia [15,16]. Moreover, there are many studies reporting a wide variability in the GVE outcomes, such as CPP relief, persistence or worsening of pain after GVE, and coil migrations and protrusions [16-19]. It was found that 6% to 32% of patients do not achieve significant pain relief after the procedure [20]. Most studies of GVE in PeVD only acknowledge the fact of complications, but do not investigate their causes [9,10,15,17]. To date, only few studies were performed to evaluate GVR in PeVD, and they provide limited data on the complications after this procedure [13, 20, 21,22]. Therefore, it is of great interest to examine thoroughly the possible post-procedural complications in order to avoid treatment failures, to improve a certain therapeutic technique, or to abandon it altogether.

References

In this study, the pelvic veins included the gonadal, parametric, uterine, common, external and internal iliac veins.

Indications for intervention on the gonadal veins are symptoms and signs of pelvic venous disorder (pelvic pain, dyspareunia, heaviness in the hypogastric region, vulvar varicose veins) in combination with the expansion of the gonadal veins of more than 5 mm and reflux in them for more than 1 s.

The indication for intervention on the left / right common iliac vein is the presence of compression stenosis of these veins of more than 50% in combination with symptoms and signs of pelvic venous disease.

Three groups of patients will be formed.

The first will include patients with ovarian venous insufficiency, dilation of the gonadal veins of more than 10 mm and reflux along them for more than 1 s, who underwent open retroperitoneal resection and endoscopic trans- and retroperitoneal resection of the gonadal veins.

The second group will include patients with ovarian venous insufficiency, dilatation of the gonadal veins less than 10 mm and pelvic venous reflux for more than 1 s, who have undergone embolization of the gonadal veins with coils.

The third will include patients with a combination of May-Thurner-Cockett syndrome and pelvic congestion syndrome who have stenting of the common iliac veins, or stenting of the iliac veins in combination with embolization of the gonadal veins with coils.

Evaluation of the effectiveness and safety of interventions on the pelvic veins will be carried out by assessing the effect of the intervention on pelvic pain, morphological and functional state of the pelvic veins. A visual analogue scale will be used to assess the dynamics of pelvic pain after gonadal and iliac vein interventions.

The assessment of the morphological and functional state will be carried out using the results of transabdominal and transvaginal duplex ultrasound (diameter of the pelvic veins, linear blood flow velocity through them, the presence of reflux in these veins and its duration).

The assessment of the safety of interventions on the pelvic veins will be carried out by assessing the severity of post-procedural pain, the frequency of complications of operations on the pelvic veins, and complications of anesthesia.

Postoperative / Postprocedural pain was assessed using a visual analogue scale.

Complications of gonadal and iliac vein interventions were assessed within 1-30 days after surgery. Complications of gonadal vein resection included:

1. Wound infectious complications;
2. Thrombosis of non-targeted pelvic veins (parametric, uterine, internal iliac veins);
3. Bleeding with the formation of a retroperitoneal hematoma after surgery;
4. Massive bleeding during surgery;
5. Intestinal paresis (ileus).

Complications of gonadal vein embolization with coils included:

1. Hematoma / bleeding at the access point;
2. Thrombosis of non-targeted pelvic veins (parametric, uterine, internal iliac veins);
3. Postembolization syndrome;
4. Protrusion of spirals;
5. Migration of spirals;
6. Allergic reactions to contrast agent or nickel.

Complications of stenting of the common iliac vein included:

1. Hematoma / bleeding at the access point;
2. Stent thrombosis;
3. Migration of the stent;
4. Perforation of the iliac veins or inferior vena cava.

The study flow chart is presented in Figure 1.

In addition, the duration of pelvic vein interventions will be compared with the length of time the patient is in hospital.

Based on this study of data, objective information will be obtained on the effectiveness and safety of interventions on the gonadal and iliac veins, and an algorithm will be proposed for determining the choice of the method of interventions on the pelvic veins in patients with pelvic venous disorders

[figure not shown]

Figure 1. The study flowchart.

1. *Clinical examination* includes obtaining information on complaints and medical history data, physical examination, assessment of local vascular status and severity of pain (using a visual analogue scale).
Clinical examination is carried out before GVE, GVR or stenting of the CIV and on days 1, 10 and 30 after the intervention.
2. *Transabdominal and transvaginal ultrasound examination of the pelvic veins and duplex ultrasound examination of the veins of the lower extremities* are performed before EEGV and on days 1, 10 and 30 after the intervention. In the absence of PES, ultrasound examinations are performed in the outpatient settings, otherwise, they are performed in the surgical hospital.
3. *Multislice computed tomography and multiplanar venography of the pelvic veins* is performed in all patients prior to interventions on the pelvic veins. Repeated computed tomography is performed if pain persists for 10 days after EEGV. It is carried out in order to exclude perforation of the vein with a coil, and to detect retroperitoneal hematoma.
4. *GVE* was performed under local anesthesia with 5.0-10.0 mL of 0.5% lidocaine solution with a patient under intravenous sedation. For the left GV embolization, the transfemoral approach was used, while for the right or both GV embolization, the transjugular approach was used.

The vein puncture was performed under ultrasound guidance. The 5F multipurpose angiographic catheters (Cordis; USA), standard ‘moving core’ J .035” guidewire, and an angled hydrophilic guidewire (Radiofocus; Terumo Corp., Japan) were used. For the GV occlusion, the pushable 0.035” standard stainless steel coils (Gianturco; William Cook, Bjæverskov, Denmark) and 0.035” coils made of Inconel with interwoven long collagen fibrils (MReye; Cook Medical Inc., Bloomington, USA) were used. The diameter of coils was 8-12 mm, and the length was 10-20 cm. When selecting the coil size, the principle of 20% coil oversizing relative to the GV diameter was used in order to avoid coil migration in the conductive veins and pulmonary artery. After embolization, the control ovarian venography was performed.

5. *Open retroperitoneal GVR* was performed under general anesthesia in the reverse Trendelenburg position, on the back with the operating table rotating 30° to the right or left, depending on the side of the GV lesion. The retroperitoneal approach was employed in the left and/or right iliac region (depending on the side of the GV lesion) with an incision of 5 to 7 cm, the GV was mobilized for 10-12 cm and its tributaries were ligated. The vein was ligated at the caudal and cranial segments and resected. Surgical wound was sutured in layers. Drainage of the retroperitoneal space was not used.
6. *Transperitoneal endoscopic GVR* was performed under general anesthesia in the reverse Trendelenburg position, on the back with the operating table turning 30 ° to the right or left, depending on the intervention side. After carbon dioxide (CO₂) insufflation into the peritoneal cavity (intraabdominal pressure 12 mm Hg), three ports were placed: one 10-mm port in the umbilical region, one 5-mm port in the left or right iliac region, and one 5-mm port 5 cm below the umbilicus. The parietal peritoneum was dissected, the GV was mobilized over a length of 10-12 cm, the GV tributaries were ligated, the caudal and cranial segments of the vein were clipped or ligated, and the vessel was resected. The wounds were sutured, and no drainage was used.
7. *Retroperitoneal endoscopic GVR* was performed under general anesthesia, and the carbon dioxide insufflation into the retroperitoneum (pressure 12 mm Hg) was applied using a Veress needle in a patient lying on the left or right side in the reverse Trendelenburg position. A 10-mm camera port was installed in the lumbar region between the posterior superior iliac spine and the lower edge of the XII rib. Then one or two 5-mm instrument ports were installed. The GV was mobilized over a length of 10-12 cm, the GV tributaries were ligated, the caudal and cranial segments of the vein were clipped, and the vessel was resected. The wounds were sutured, and no drainage was used.

8. *Stenting of the left common iliac vein.* After providing local anesthesia, the left common femoral vein was punctured, a 0.035" guidewire was inserted into the inferior vena cava (IVC), and then a 10F introducer was installed. A balloon catheter was introduced over the guidewire in the left CIV (XXL balloon, Boston Scientific, diameter 14-18, length 40-60 mm), and double balloon dilation of the vessel was performed with a pressure of 6-8 atm. Then, a delivery system was advanced to the area of stenosis in the left CIV, and stent was deployed at the level of confluence of the left CIV and inferior vena cava (IVC) or with a protrusion in the IVC of no more than 1 cm. For better fixation of stent in the venous lumen and prevention of its displacements and migration, a balloon post-dilatation of the stented vessel was performed. In case of residual stenosis, the balloon angioplasty was performed. A control multiplanar phlebography was repeated thereafter.

All interventions were performed in surgical clinic settings. The routine anticoagulation to prevent thromboembolic complications after the procedure was not prescribed. All patients used antiembolism compression stockings before and after the interventions. Patient mobilization after GVE or GVR started 2 hours after the intervention.

9. *Medical therapy:*

A) *Anti-inflammatory and analgesic therapy:* all patients receive one injection of diclofenac 75 mg intramuscularly on the next day after interventions.

B) *Venoactive drug treatment:* micronized purified flavonoid fraction (MPFF) 1000 mg once daily. This drug has been chosen because of its pharmacological properties, clinical effects, and personal experience of its use in patients with PeVD and without an indication for any intervention on the gonadal veins.

C) After stenting, all patients received anticoagulant therapy for the prevention of venous thromboembolic events for 1 month (enoxaparin sodium or nadroparin calcium subcutaneous injections into the abdominal wall in a dose of 1 mg per 1 kg of body weight once daily), as well as antiplatelet drugs (clopidogrel 75 mg) for 3 months after intervention.

All data obtained during the clinical examinations, ultrasound and radiation examinations are recorded in the individual case report form (CRF).

References

4. Katsenis, K. Micronized purified flavonoid fraction (MPFF): A review of its pharmacological effects, therapeutic efficacy and benefits in the management of chronic venous insufficiency. *Curr. Vasc. Pharmacol.* 3, 1–9 (2005).

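### Repeat CT is written only for embolization, while its target, retroperitoneal hematoma, is listed as a complication only for resection, so complication rates may differ by how events are found and counted

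*Combined protocol and SAP*

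**What the plan says.** The examination schedule in Methodology has three relevant items.

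- Item 1, clinical examination, names all three procedures: "Clinical examination is carried out before GVE, GVR or stenting of the CIV and on days 1, 10 and 30 after the intervention".
- Item 2, ultrasound, uses EEGV for the baseline scan only. The examinations "are performed before EEGV and on days 1, 10 and 30 after the intervention".
- Item 3, CT and venography, "is performed in all patients prior to interventions on the pelvic veins". The repeat scan is narrower: "Repeated computed tomography is performed if pain persists for 10 days after EEGV". Its purpose is stated: "It is carried out in order to exclude perforation of the vein with a coil, and to detect retroperitoneal hematoma".

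The complication lists come just before these items. The GVR list includes "Bleeding with the formation of a retroperitoneal hematoma after surgery". For bleeding, the GVE and stenting lists have only hematoma or bleeding at the puncture site. Perforation of a vein is listed for stenting but not, under that name, for GVE.

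The project summary adds a second layer. GVE complications are graded by SIR classes A to F, and GVR complications are judged by general surgical principles. The statistical section compares categorical outcomes by chi-square and models postoperative complications by logistic regression. It does not mention differences in how events were ascertained.

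**The concern.** Complication rates by procedure are a stated aim, and the results are to feed an algorithm for choosing the procedure. A comparison of rates needs events to be looked for and counted in the same way in each group. As written, a woman whose pain persists 10 days after embolization gets a CT that can show a retroperitoneal hematoma. No such scan is written for a woman with the same pain after resection. Yet the event sits on the resection list and not on the embolization list. The first feature would raise the GVE count relative to GVR, and the second would lower it. The chi-square test and the regression would take whatever results as a difference in risk.

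**Working it through.** **1. The plan's own figures.** The documents give no complication rate, group size, alpha or power. The only number is a total of 300 patients, without derivation, so there is nothing to reproduce. The check is a comparison of text, followed by an illustration.

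**2. The text side by side** (Methodology schedule and lists; project summary for grading).

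| Element | GVR | GVE | Stenting |
|---|---|---|---|
| Clinical examination, days 1, 10, 30 | named | named | named |
| Follow-up ultrasound, days 1, 10, 30 | no procedure named | no procedure named | no procedure named |
| Baseline CT | all patients | all patients | all patients |
| Repeat CT for persisting pain | none written | written | none written for stenting alone |
| Retroperitoneal hematoma on list | yes | no | no |
| Vein perforation on list | not as such | not as such (coil protrusion may overlap) | yes |
| Grading | general surgical principles | SIR A to F | none stated |

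GVE and GVR differ in three rows: the repeat CT trigger, the listing of its hematoma target, and the grading system. SIR class A, which needs no treatment and has no consequences, counts as a minor complication. A harmless finding can therefore be classed after GVE, and no parallel class is given for GVR.

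**3. What unequal recording can do to the test.** Assumptions, none from the documents: two groups of n patients; the same true rate p of one complication; all events recorded in one group and a share s in the other; two-sided chi-square at 0.05 without continuity correction. An equal three-way split gives n = 300/3 = 100.

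The observed rates are p and s × p. For example, p = 5% and s = 0.5 give 5% against 2.5%. With x and y recorded events,

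z = [(x − y)/n] / √[p̄(1 − p̄) × 2/n], where p̄ = (x + y)/(2n).

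The chance of a false finding is the sum of Bin(x; n, p) × Bin(y; n, sp) over all pairs with |z| > 1.96.

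| s (n = 100) | p = 5% | p = 10% | p = 20% |
|---|---|---|---|
| 1 | 4.4% | 5.2% | 5.1% |
| 0.75 | 6.1% | 9.8% | 15.6% |
| 0.5 | 13.2% | 27.0% | 51.8% |
| 0.25 | 31.2% | 60.9% | 92.1% |
| 0 (not countable in one group) | 74.2% | 99.2% | 100% |

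Hand check of the 74.2% cell: with s = 0, y is always 0. At x = 3, z = 0.03/√(0.015 × 0.985 × 0.02) = 1.75. At x = 4, z = 0.04/√(0.02 × 0.98 × 0.02) = 2.02. So the test rejects when x ≥ 4, and P(X ≥ 4) for Bin(100, 0.05) is 0.742.

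With n = 150 (300/2, the limit if almost nobody were in the stenting group) and s = 0.5, the three chances are 19.5%, 37.0% and 68.6%.

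**4. Direction.** For retroperitoneal hematoma, the extra CT raises detection after GVE, and its absence from the GVE list lowers the GVE count. The documents give nothing with which to net these off.

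**The case against.** The best defence is that the wording is loose rather than the design unequal. The lists are introduced as what complications included, not as closed lists. SIR classes rest on treatment and consequence, so they could admit a retroperitoneal hematoma after GVE. Imaging findings from all examinations go into the case report form. Figure 1, the flowchart, is not visible here and might assign examinations by group. Much of this stands, and it rules out several stronger readings.

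- A reader might infer that duplex follow-up was for embolization only, so that thrombosis is over-detected after GVE. The text does not support this. Only the baseline scan is tied to EEGV, and the follow-up days are counted from the intervention. The study aim applies ultrasound to all three procedures, and Methodology does not restrict it: "The assessment of the morphological and functional state will be carried out using the results of transabdominal and transvaginal duplex ultrasound". The rule beginning "In the absence of PES, ultrasound examinations are performed in the outpatient settings" governs where the scan is done, not whether. This is ambiguity, not a restriction.
- A reader might infer that a retroperitoneal hematoma after GVE cannot be counted at all. That is true of the Methodology list but not established for the study, given SIR.
- A reader might infer that hematoma was not looked for after GVR. Clinical examination names GVR, and ultrasound follows the intervention. Only the repeat CT trigger is missing.

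What the defence does not answer is which source decides the count. It also leaves unexplained why the repeat CT names one procedure when item 1 names three.

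**Conclusion.** The point holds in a limited form. Repeat CT is written only for persisting pain after EEGV, which by its purpose is embolization. One of its two stated targets, retroperitoneal hematoma, is listed for GVR and not for GVE or stenting, and the documents do not say whether the lists or the SIR classes govern. Complication rates may therefore differ between groups because of detection and listing rules. That they do differ, by how much, and in whose favour cannot be shown from the documents. The percentages in the working show how sensitive the chi-square test is under assumed rates, shares and group sizes. They are not estimates for this study, and rarer events would give smaller chances. The point should be settled before rates are compared. It does not invalidate the study.

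**What to change.** 1. Define EEGV and reconcile Methodology items 2 and 3 with the procedures that were actually imaged. This is a matter of describing the records, not of setting an imaging rule.
2. For between-group comparisons and the regression outcome, use one common complication list for all three groups, including retroperitoneal hematoma and vein perforation. State that this list decides what is counted and that SIR is used for grading only.
3. Report the number of patients with repeat CT in each group, and flag events found only by repeat CT.
4. Repeat the comparison without the flagged events as a sensitivity analysis.

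Restricting the main comparison to clinically overt events would not do the same job. Repeat CT is triggered by pain, so what it finds is already symptomatic and would stay in the GVE count.

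The cost is a little more abstraction from existing records, since imaging results are already recorded in the case report form, and fewer events in the sensitivity analysis.
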